3.8 Safety Analyses

Safety analyses will be conducted for the safety population. Summaries will be prepared for the targeted safety endpoints listed in the secondary endpoints and for all observed AEs organized by body system. The CIT consortium modified the National Cancer Institute (NCI) toxicity table to create a document relevant for trials of adult pancreatic islet transplantation. The resulting reference manual, "Terminology Criteria for Adverse Events (TCAE) In Trials of Adult Pancreatic Islet Transplantation," provides descriptive terminology and a grading (severity) scale which will be utilized for adverse event (AE) reporting.

Regular safety analyses will be prepared for the Data Safety Monitoring Board (DSMB). These summaries will be used to monitor the overall safety profile of the study. These analyses will summarize all AE data that are available at the time of the DSMB meeting. Analyses will summarize AEs by Medra term and body system. Separate incidence summaries will be prepared for serious AEs, for nonserious AEs and for all AEs combined. Separate tables will summarize severity and attribution. Each AE can be attributed to the investigational agent (allogeneic islets), the immunosuppression, both or neither. Identical safety summaries will be included in the final statistical report.

The protocol also describes targeted safety endpoints. The planned analyses for general safety outcomes and for these targeted safety endpoints are described in the following few sections.

3.8.1 Adverse Events

An AE is any occurrence or worsening of an undesirable or unintended sign, symptom (including an abnormal laboratory finding), or disease that is temporally associated with the use of a medicinal product whether considered related to the medicinal product or not. An SAE is defined as any AE occurring at any dose that suggests a significant hazard, contraindication, side effect, or precaution. This includes but is not limited to any of the following events (21CFR§312.32):

- Death.
- A life-threatening event. A life-threatening event is any adverse therapy experience that, in the view of the investigator, places the patient or participant at immediate risk of death from the reaction as it occurred.
- Inpatient hospitalization or prolongation of existing hospitalization.
- Persistent or significant disability.
- Congenital anomaly or birth defect.
- An event that required intervention to prevent permanent impairment or damage. An important medical event that may not result in death, be life threatening, or require hospitalization may be considered an SAE when, based on appropriate medical judgment, it may jeopardize the participant and may require medical or surgical intervention to prevent one of the outcomes listed above.
- Other conditions specified in the protocol.

In addition, events that occur at a higher than expected frequency, as determined by appropriate medical judgment, may be considered SAEs.

AEs will be graded on a scale from 1 to 5 according to the following standards in the *CIT-TCAE* manual:

Grade 1 = Mild adverse event.

Grade 2 = Moderate adverse event.

Grade 3 = Severe and undesirable adverse event.

Grade 4 = Life-threatening or disabling adverse event.

Grade 5 = Death.

AEs not included in the CIT-TCAE listing, will be recorded and graded 1 to 5 according to the General Grade Definition provided as in the table below:

Table 8-General Severity Definition of Adverse Event

Grade	Description	Definition
Grade 1	Mild	Transient or mild discomforts (<48 hours), no or minimal medical intervention/therapy required, hospitalization not necessary (non-prescription or single-use prescription therapy may be employed to relieve symptoms, e.g., aspirin for simple headache, acetaminophen for post surgical pain).
Grade 2	Moderate	Mild to moderate limitation in activity some assistance may be needed; no or minimal intervention/therapy required, hospitalization possible.
Grade 3	Severe	Marked limitation in activity, some assistance usually required; medical intervention/therapy required hospitalization possible.
Grade 4	Life-threatening	Extreme limitation in activity, significant assistance required; significant medical/therapy intervention required hospitalization or hospice care probable.
Grade 5	Death	Death.

All AEs will be reported and graded whether they are or are not related to disease progression or treatment. The relationship of an AE to islet transplantation, which includes the transplant procedure and/or the islet product, or to the immunosuppression and/or infection prophylaxis will be defined by using the descriptors provided in Table 9.

Table 9 -Attribution of Adverse Event

Code	Description	Definition
UNRELATED CATEGORY		
1	Unrelated	This adverse event is clearly not related to allogeneic islets; the islet transplant procedure; immunosuppression or infection prophylaxis.
RELATED CATEGORIES		
2	Unlikely	The adverse event is doubtfully related to allogeneic islets; the islet transplant procedure; immunosuppression or infection prophylaxis.
3	Possible	The adverse event may be related to allogeneic islets; the islet transplant procedure; immunosuppression or infection prophylaxis.
4	Probable	The adverse event is likely related to allogeneic islets; the islet transplant procedure; immunosuppression or infection prophylaxis.
5	Definite	The adverse event is clearly related to allogeneic islets; the islet transplant procedure; immunosuppression or infection prophylaxis.

The collecting and recording procedures for AEs are described in detail in Section 8.2 of CIT-07 protocol.

3.8.2 Analysis of Secondary Endpoints for Safety

The safety secondary endpoints in this study target AEs related to islet transplantation (transplant procedure and/or islet product) and the immunosuppression and/or infection prophylaxis.

The targeted AEs related to the islet transplantation include:

1. AE-IIP-1: Bleeding (>2 g/dL decrease in hemoglobin concentration)
2. AE-IIP-2: Segmental portal vein thrombosis
3. AE-IIP-3: Biliary puncture
4. AE-IIP-4: Wound complication (infection or subsequent hernia)
5. AE-IIP-5: Increased transaminase levels (>5 times ULN)

The targeted AEs related to the immunosuppression and infection prophylaxis therapy include:

1. AE-IP-1: Allergy
2. AE-IP-2: Reduction in GFR
3. AE-IP-3: Increase in urinary albumin excretion
4. AE-IP-4: Addition or intensification of anti-hypertensive therapy
5. AE-IP-5: Addition or intensification of anti-hyperlipidemic therapy
6. AE-IP-6: Oral ulcers
7. AE-IP-7: Lower extremity edema
8. AE-IP-8: Gastrointestinal toxicity
9. AE-IP-9: Neutropenia, Anemia, or Thrombocytopenia
10. AE-IP-10: Viral, Bacterial, or Fungal Infections
11. AE-IP-11: Benign or Malignant Neoplasms

3.8.2.1 Analyses at 75±5 days following the initial and final infusion

At 75±5 days following the initial and final islet transplant (if applicable), the incidence rates for each type of AE, grouped by severity, will be reported. For each type of AE, the number of resolved events will be counted as well. The mean, median, standard deviation and range for the number of days until the AE is resolved will be calculated. The results will be summarized in the table provided in SAP Appendix 2. Moreover, we will also report AEs categorized by attribution that is, AEs related to the islet transplant procedure or to immunosuppression; the report format is shown in SAP Appendix 3.

For second and third islet transplants, immunosuppression is modified by using Daclizumab (Zenapax[®]) instead of Thymoglobulin[®] for induction. For subjects who receive more than one islet transplant, we will compare the incidence rate at 75±5 days following the initial and final islet transplant for all AEs related to the islet transplant procedure and to immunosuppression one at a time using the McNemar's matched-pair test [8]. The claim of a difference in incidence rate will be made if the p-value is less

than 0.05. If the incidence is rare in certain severity categories for an AE, we will compare the incidence rate regardless the severity to accommodate the validity of the test.

The incidence rate of immune sensitization, defined as detection of anti-HLA antibodies at 75 ± 5 days following the initial and final islet transplant, (if applicable) will be reported. The exact two-sided 95% confidence interval of the incidence rate will also be reported.

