3.8.2.2 Analyses at 365±14 days following the initial and final infusion

At 365±14 days following the initial and final islet transplant (if applicable), the incidence rates for each type of AE, grouped by severity, will be reported. For each type of AE, the number of resolved events will be counted as well. The mean, median, standard deviation and range for the number of days until the AE is resolved will be calculated. The results will be summarized in the table provided in Appendix 3. Moreover, we will also report the individuals who incur the AEs related to the islet transplant procedure and immunosuppression therapy, and the report is given in the table described in Appendix 3.

For subjects who require more than one islet transplant, we will compare the incidence rate at 365±14 days following the initial and final islet transplant for all the AEs related to the islet transplant procedure and immunosuppression therapy one at a time using the McNemar's matched-pair test [8]. The claim of difference in incidence rate will be made if the p-value is less than 0.05. If AE incidence is rare in certain severity categories, we will compare the incidence rate regardless of the severity to accommodate the validity of the test.

Adverse events may require a change in the immunosuppression for an individual transplant recipient. We will document the number and proportion of participants who require such a change.

For subjects who do not present the anti-HLA antibodies prior to transplantation, we will calculate the incidence rate of immune sensitization defined by detecting anti-HLA antibodies at 365±14 days following the initial and final islet transplant, (if applicable). The exact two-sided 95% confidence interval of the incidence rate will also be reported.

At 365±14 days following the initial islet transplant, we will also assess the change in retinal photography from pre-transplant. The incidence rate of worsening retinopathy will be calculated and the exact two-sided 95% confidence interval of the rate will be provided.

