3.8.3 Statistical Analyses of Adverse Events

AEs will be analyzed according to the body system described in the *CIT-TCAE* manual. Any event that appears in a body system will be categorized into one of the five severity grades according to the *CIT-TCAE* manual or the general definition of severity given in Table 7 and analyzed accordingly. For each event, we will analyze its incidence rate per 100 person-days. Suppose for each subject, the incidence of a particular event is a Poisson process with the homogeneous incidence rate λ . At the time of analysis, if a subject is only followed r days after the randomization, the incidence of this event is distributed according to the Poisson distribution with mean $r\lambda/100$. The maximum

likelihood estimate of the incidence rate will be obtained based on data collected from the available subjects at the analysis time. The 95% confidence interval derived using the maximum likelihood estimator theory will be also reported. The results will be summarized in the table provided in SAP Appendix 4. Moreover, we will also list all the individuals who have ever had an incident of any of the AEs listed in Appendix 5 since their randomization.

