5. HFS							
n							
mean							
s.d.							
median							
range							

Appendix 2 - Summary Table of Adverse Events Related to the Islet transplant and Immunosuppression Therapy

Events	Degrees of Event Severity					Total
	Grade 1	Grade 2	Grade 3	Grade 4	Grade 5	
AE related to the islet transplantation (islet product or islet transplant procedure):						
AE-IIP-1 Number (%) Resolved? Number (%) mean s.d. median min-max						
AE-IIP-2 Number (%) Resolved? Number (%) mean s.d. median min-max						
AE-IIP-3 Number (%) Resolved? Number (%) mean s.d. median min-max						
AE-IIP-4 Number (%) Resolved? Number (%) mean s.d. median min-max						
AE-IIP-5 Number (%) Resolved? Number (%) mean s.d. median min-max						
AE related to the immunosuppression and/or infection prophylaxis:						
AE-IP-1 Number (%) Resolved? Number (%) mean s.d.						

median min-max AE-IP-2 Number (%) Resolved? Number (%) mean s.d. median min-max AE-IP-3 Number (%) Resolved? Number (%) mean s.d. median min-max AE-IP-4 Number (%) Resolved? Number (%) mean s.d. median min-max AE-IP-5 Number (%) Resolved? Number (%) mean s.d. median min-max AE-IP-6 Number (%) Resolved? Number (%) mean s.d. median min-max AE-IP-7 Number (%) Resolved? Number (%) mean s.d. median min-max AE-IP-8 Number (%) Resolved? Number (%)						
--	--	--	--	--	--	--

mean s.d. median min-max AE-IP-9 Number (%) Resolved? Number (%) mean s.d. median min-max AE-IP-10 Number (%) Resolved? Number (%) mean s.d. median min-max AE-IP-11 Number (%) Resolved? Number (%) mean s.d. median min-max						
---	--	--	--	--	--	--

**Appendix 3 - Adverse Events: Number Observed and Rate with Patient
Identifications Grouped by Severity and Attribution**

Events	Degrees of Event Severity					Total
	Grade 1	Grade 2	Grade 3	Grade 4	Grade 5	
AE related to the islet transplantation (islet product or islet transplant procedure):						
AE-IIP-1 incidences	6 (12.5%) C11+ C12 C22 C34 C63 C66					
AE-IIP-2 incidences						
AE-IIP-3 incidences						
AE-IIP-4 incidences						
AE-IIP-5 incidences						
AE related to the immunosuppression and/or infection prophylaxis:						
AE-IP-1 incidences						
AE-IP-2 incidences						
AE-IP-3 incidences						
AE-IP-4 incidences						
AE-IP-5 incidences						
AE-IP-6						

incidences						
AE-IP-7 incidences						
AE-IP-8 incidences						
AE-IP-9 incidences						
AE-IP-10 incidences						
AE-IP-11 incidences						

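### Days to adverse-event resolution are summarised with no rule for events still open, so the duration of persistent events is understated

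*SAP*

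**What the plan says.** Section 3.8.2.1 sets the Day 75 safety analysis: "At 75±5 days following the initial and final islet transplant (if applicable), the incidence rates for each type of AE", by severity, are to be reported. It then counts the resolved events and adds "The mean, median, standard deviation and range for the number of days until the AE is resolved will be calculated". Section 3.8.2.2 repeats both steps at Day 365, including "For each type of AE, the number of resolved events will be counted as well".

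The Day 75 results go to Appendix 2, whose shell for each event type reads "AE-IIP-1 Number (%) Resolved? Number (%) mean s.d. median min-max" across five grades and a total. For Day 365 the text says "The results will be summarized in the table provided in Appendix 3". The Appendix 3 shell holds only incidences and patient identifiers. It has no resolved-count row and no duration row.

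The SAP has no censoring rule for duration, no time-to-event estimate, no stated denominator and no rule on resolution dates after the window. Section 3.8.3 does allow for partial follow-up ("At the time of analysis, if a subject is only followed r days after the randomization"), but only in the incidence rate. Section 3.8.1 leaves some AE matters to the protocol: "The collecting and recording procedures for AEs are described in detail in Section 8.2 of CIT-07 protocol". That covers collection and recording, not the analysis of duration.

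**The concern.** Time to resolution is a time-to-event quantity, and some events will be open when the data are summarised. A simple mean or median cannot include an event that has no end date. The events left out are the longest, so what remains is a sample selected for being short.

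The effect differs by event type. A brief procedural event will nearly always have ended by the cut-off. Several targeted events could plausibly outlast 75 days, such as "AE-IP-2: Reduction in GFR" or an increase in urinary albumin excretion. Section 2.2.1 makes safety part of the primary objective, and Section 1 says the benefit must justify the risks of the procedure and the immunosuppression. How long a harm lasts is part of that judgement.

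The silence on later resolution dates is a second problem. Two analysts following the text could cut the data at the window or use all later dates, and report clearly different durations from the same records.

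**Working it through.** The plan gives no figure for AE duration, so there is none to reproduce. The check asks what a resolved-only summary shows when the true duration is known.

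**Inputs from the SAP.** Cut-offs T = 75 and T = 365 days (Sections 3.8.2.1 and 3.8.2.2). Follow-up to 24 months after the final transplant (Section 3.1.1), taken here as about Day 730.

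**Assumptions.** Durations are exponential with mean m. Onset is uniform over the window, or at Day 0 as the case more favourable to the plan.

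**Formulas, uniform onset, data cut at T.** With a = T/m:

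- Share resolved: P = 1 − (1 − e^(−a))/a
- Mean among resolved: M = { m[1 − (1 + a)e^(−a)] − (m²/T)[2 − (a² + 2a + 2)e^(−a)] } / P

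Example, T = 75 and m = 60: a = 1.25 and e^(−a) = 0.2865. P = 1 − 0.7135/1.25 = 0.429. The numerator is 60 × 0.3554 − 48 × 0.2631 = 21.32 − 12.63 = 8.69. M = 8.69/0.429 = 20.3 days.

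| True mean (days) | Day 75: mean shown | Day 75: resolved | Day 365: mean shown | Day 365: resolved |
|---|---|---|---|---|
| 14 | 10.9 | 81% | 13.4 | 96% |
| 30 | 16.5 | 63% | 27.3 | 92% |
| 60 | 20.3 | 43% | 48.4 | 84% |
| 120 | 22.5 | 26% | 73.7 | 69% |
| 240 | 23.7 | 14% | 94 | 49% |

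As m grows, M tends to T/3, which is 25 days at Day 75 and about 122 days at Day 365. The Day 75 mean is therefore almost flat once true durations pass about 60 days.

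**Onset at Day 0, T = 75.** M = [m − (T + m)e^(−T/m)]/(1 − e^(−T/m)). For m = 14 this is (14 − 89 × 0.00471)/0.9953 = 13.6 days, close to the truth. For m = 60, 120 and 240 it gives 29.9, 33.6 and 35.6 days.

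**Resolution dates used to Day 730.** With onset uniform on (0, W) and cut-off C, average over onset o both the resolved share, 1 − e^(−(C−o)/m), and the numerator, m − (C − o + m)e^(−(C−o)/m), then divide the second average by the first.

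| True mean (days) | Shown, onset in first 75 days | Shown, onset in first 365 days |
|---|---|---|
| 60 | 60 | 60 |
| 120 | 118 | 113 |
| 240 | 199 | 176 |

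**Does censoring repair it?** Kaplan-Meier medians were computed with uniform onset, open events censored at the window, and 200,000 simulated events per case.

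| Cut-off | True median | Resolved-only median | Kaplan-Meier median |
|---|---|---|---|
| Day 75 | 20.8 | 12.6 | 20.7 |
| Day 75 | 62.4 | 18.1 | 62.5 |
| Day 75 | 124.8 | 20.0 | not reached |
| Day 365 | 62.4 | 46.4 | 62.7 |
| Day 365 | 124.8 | 67.5 | 124.8 |

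Kaplan-Meier recovers the true median where the data can support one and says so where they cannot.

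**The case against.** Much of the opposing case stands.

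- **The cap at the window is not stated.** A reader might infer that the plan truncates every duration at 75 or 365 days. The SAP fixes the time of the analysis but does not say that later resolution dates are discarded, and follow-up runs well beyond. The large figures hold only under that reading.
- **Persistent harms are not hidden.** A reader might infer that the tables cannot tell a 60-day harm from a 240-day one. At Day 365 the means differ (48 against 94 days). At Day 75 the means nearly coincide, but the resolved share does not (43% against 14%), and Appendix 2 prints that share above the duration rows. The share still does not correct the mean or median beneath it, and at Day 365 the named table has no place for it.
- **The figures rest on assumed distributions.** Uniform onset suits infusion-related events poorly, and short events show little bias with onset at Day 0 or at the Day 365 cut-off. That particular targeted events persist is also an assumption.
- **Nothing decisive depends on it.** Section 2.3.2.3 defines the safety endpoints largely by incidence and severity. No test or stopping rule in the SAP uses days to resolution. A reader might infer that the Data Safety Monitoring Board (DSMB) would be misled, but duration is not among the DSMB summaries listed in Section 3.8.
- **Kaplan-Meier in every Appendix 2 cell would not work.** There are 5 + 11 = 16 event types and 5 grades, so 80 cells for about 48 subjects.

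These points limit the size of the concern and shape the remedy. They do not supply the missing rule for open events or the missing cut-off.

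**Conclusion.** The point holds in a limited form. As written, days to resolution can be computed on resolved events only, and the SAP does not say which resolution dates count. The direction of the bias is certain: durations are understated, and more so the longer the event lasts.

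The size is conditional on the assumed exponential durations. With uniform onset and data cut at the window, true means of 60 to 240 days all read about 20 to 24 days at Day 75, and 48 to 94 days at Day 365. If dates to about Day 730 are used and onset falls in the first 75 days, the same events read about 60 to 199 days. A 14-day event reads 13.4 days at Day 365 with uniform onset.

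The measure is descriptive, so no efficacy conclusion or trial decision changes. It still merits correction, because the repair is cheap and the present statistic is least reliable for the most persistent harms. The reference to Appendix 3 in Section 3.8.2.2 is a separate, plain error for the resolution results.

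**What to change.** In Sections 3.8.2.1 and 3.8.2.2:

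1. State the data cut-off for resolution dates, and use all available follow-up in the final report.
2. For each event type, pooled over grades, report the number of events still open at the cut-off and the Kaplan-Meier median time from onset to resolution, or that it was not reached. Censor open events at last follow-up. Count an event open at death as not resolved, kept at risk to the end of the analysis period.
3. Label any mean, SD or range that is kept as among resolved events only.
4. Leave out items with no meaningful resolution date. Added or intensified anti-hypertensive and anti-hyperlipidemic therapy are candidates.
5. Correct the table reference in Section 3.8.2.2 so that the resolution results go to Appendix 2, and add rows there for the open count and the Kaplan-Meier median.

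The cost is a short paragraph and two table rows. It needs onset, resolution and last-contact dates; their recording is left to the protocol, so this should be confirmed. For rare events the median will often be imprecise or not reached, which reflects what the data can support.

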3.1 Study Period and Visit Window Definition

3.1.1 Study Period

The trial consists of three periods: (1) the pretransplant period, which includes screening, enrollment, and wait list time; (2) the period that includes the islet transplant procedure(s); and (3) follow-up visits through 24 months following the final transplant. The study period of this trial is a 24-month follow-up after the final islet transplant. Subjects may undergo up to 3 transplants in the course of this study; the final transplant can occur not later than 8 months following the first transplant.

In the first period, individuals who meet the general inclusion criteria will be approached regarding participation in the study. After informed consent has been obtained, they will be formally enrolled into the study. Eligibility will be confirmed based on the results of the screening visit procedure detailed in Appendix 1 of the CIT-07 protocol. Enrolled subjects who meet the eligibility screening for the studies will be put on the waiting list for an islet transplant.

Once a compatible islet preparation becomes available, a subject's eligibility will be re-confirmed and eligible subjects will begin immunosuppression therapy on Day -2 (Day 0 is defined as the day of transplant).

During the post-transplant follow-up period, subjects may receive up to two additional transplants. After receiving his/her initial islet transplant, if a subject does not meet the criteria for insulin independence described in Section 4.1.2 of the CIT-07 protocol, but has either a basal or stimulated C-peptide level ≥ 0.3 ng/mL (0.1 nmol/L), s/he will be considered for a second islet transplant. A second islet transplant will be considered at 75 ± 5 days after the first islet transplant and when all required metabolic assessments are complete. If, after the second islet transplant, both basal and stimulated C-peptide levels remain <0.3 ng/mL (0.1 nmol/L), the recipient will be considered to have failed the endpoint, and immunosuppression will be managed as described in the protocol. A third islet transplant will be considered only if all the criteria described in Section 7.4 of the CIT-07 protocol are met. Islet transplant recipients who have completed 12 months of follow up after their first infusion will no longer be eligible for additional islet transplants under the CIT-07 protocol.

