3.7.8 Sensitivity Analysis

The measure of a secondary endpoints may be missing at either 75±5 days or 365±14 days or both, following the initial and final infusion (if applicable). In our analysis report for the secondary endpoints, we will not impute missing values in any of these secondary endpoints. With close monitoring and data validation, the chance of having missing values will be minimized except that some serious adverse events (SAEs) may force subjects to withdraw from the study treatment or withdraw consent without a particular reason during the study. The interpretation of our analysis is strictly applied to the efficacy measurable population. However, a sensitivity analysis will be performed to determine the potential effect that missing values have on the analyses of the secondary endpoints.

- Missing values due to SAE will be excluded from this analysis. The analysis on these subjects will be provided in SAP section 3.8.
- We will conduct a sensitivity analysis assuming a missing at random mechanism: *i.e.*, we assume that a subject will withdraw consent at random with probability r . This probability will be estimated at 75 ± 5 days and 365 ± 14 days following the initial and final infusion (if applicable). The sensitivity analysis will be conducted according to the following two templates (the assumption of missing at random cannot be verified and these results must be viewed with caution.)

For the binary secondary endpoint under consideration, we will fit a logistic regression using the complete baseline data as described in SAP section 3.6. For each missing value, we will draw the outcome randomly from the Bernoulli distribution where the probability is that estimated from the corresponding complete data logistic regression model. The proportion of the secondary endpoint where missing values have been imputed will be compared to that based on the complete data to determine the magnitude of missing values' impact. If the difference between the proportion containing imputed values and that based on complete data is large, then the impact of missing values on the analysis of the endpoint under consideration is large as well; if the difference is small, then the impact of missing values on the analysis is small as well.

We will describe the reliability of this impact using the bootstrap procedure as described below:

- 1) We will resample the complete observations with replacement 1000 times.

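### The first-versus-final adverse-event test in SAP 3.8.2.1 uses only re-infused subjects, so a difference can be claimed at p<0.05 without one for any event type that lowers the chance of re-infusion

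*SAP*

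**What the plan says.** SAP 3.8.2.1 introduces the comparison with the change of induction agent: "For second and third islet transplants, immunosuppression is modified by using Daclizumab". It continues: "For subjects who receive more than one islet transplant, we will compare the incidence rate at 75±5 days following the initial and final" infusion. Each event type related to the procedure or to immunosuppression is tested separately, "one at a time using the McNemar's matched-pair test". The decision rule is explicit: "The claim of a difference in incidence rate will be made if the p-value is less" than 0.05. SAP 3.8.2.2 repeats the test at one year: "For subjects who require more than one islet transplant, we will compare the incidence rate at 365±14 days following the initial and final" infusion. Neither section says whether the exact, uncorrected or continuity-corrected form is meant, or whether the test is one- or two-sided.

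Three other places bear on who enters the pairs.
- SAP 3.7.8, on missing secondary endpoints, expects that "some serious adverse events (SAEs) may force subjects to withdraw from the study treatment".
- SAP 3.1.1 considers a second transplant at 75±5 days, "if a subject does not meet the criteria for insulin independence" and a C-peptide condition is met. It names no adverse-event criterion, and it leaves third-transplant criteria to the protocol.
- SAP 3.1.1 also requires the final transplant within 8 months of the first.

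Outside the paired test, 3.8.2.1 reports incidence by event type and severity after the initial and the final infusion.

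**The concern.** McNemar's test compares the two kinds of discordant pair: event after the first infusion only, and event after the final infusion only. If the risk is the same at both infusions and pairs form without regard to outcome, the two counts have equal expectation. Here a subject enters the pairs only by being re-infused, and that decision follows the first outcome. The 75-day record is largely complete when a second transplant is first considered. An event that ends study treatment, or in the extreme a death, removes its subject from the pairs. An event after the final infusion cannot do so.

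The pairing therefore does not protect the comparison. At stake is a formal statement on safety. This is the only significance test in the adverse-event sections, and it follows directly on the sentence about the changed induction agent. A selection effect could be read as an effect of regimen or of repeat infusion.

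**Working it through.** The SAP gives no power, error rate or expected number of pairs for this test, so there is no stated figure to reproduce.

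**Inputs.**
- From the SAP: 48 subjects (2.1); pairs restricted to the re-infused; claim at p<0.05, taken as two-sided.
- Assumed, because the SAP gives none: true risk p, equal at both infusions (30%, with lower values as a check); re-infusion probability s0 = 0.60 without a first-infusion event; s1 with an event, varied from 0.60 down to 0.15. Events at the two infusions are independent within a subject unless stated.

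**Step 1: incidence in the pairs.** First-infusion incidence among the re-infused is p·s1 / [p·s1 + (1−p)·s0]. At p = 0.30 and s1 = 0.30 this is 0.09 / (0.09 + 0.42) = 17.6%. Final-infusion incidence in the same pairs stays at 30%. The gap of about 12 points arises with no difference in risk.

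**Step 2: discordant pairs.** The probability that a subject gives a first-only pair is p(1−p)s1, and a final-only pair (1−p)p·s0. Their ratio is s1 : s0, whatever p is. At s1 = 0.30 the expected counts are 48 × 0.21 × 0.30 = 3.0 and 48 × 0.21 × 0.60 = 6.0, among 48 × 0.51 = 24.5 pairs.

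**Step 3: false-claim rate.** With those two cell probabilities, the trinomial distribution over 48 subjects was summed over every outcome with McNemar p<0.05. At p = 0.30 and s0 = 0.60:

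| s1 | first-infusion incidence in pairs | false claim, uncorrected | false claim, exact |
|---|---|---|---|
| 0.60 (no selection) | 30.0% | 4.4% | 2.5% |
| 0.48 | 25.5% | 5.6% | 3.2% |
| 0.45 | 24.3% | 6.4% | 3.7% |
| 0.30 | 17.6% | 15.0% | 9.3% |
| 0.15 | 9.7% | 36.9% | 23.8% |

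Simulation of 20,000 trials per setting agrees (14.8% and 9.1% at s1 = 0.30).

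**Step 4: where the effect shrinks or turns.**
- Event that leaves re-infusion unchanged: s1 = s0, and there is no bias.
- Risk 5%, re-infusion halved to 0.30: 2.6% uncorrected and 0.1% exact, the same as with no selection, because discordant pairs are too few.
- Risk 12.5%, re-infusion halved: 10.0% and 2.6%, against 4.7% and 1.4%. For an event of this frequency the excess depends heavily on the form of the test.
- Risk 30%, s1 = 0.30, within-subject correlation 0.3: about 12% and 5%. The effect is smaller but remains.
- Event that makes re-infusion more likely (s0 = 0.40, s1 = 0.80, risk 30%): first-infusion incidence in the pairs is 0.24 / (0.24 + 0.28) = 46%, and the false claims (19.4% and 13.5%) point the other way.

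**Step 5: the 365-day comparison.** The final transplant falls no later than 8 months after the first. In every re-infused subject, the one-year window after the first infusion therefore contains at least 12 − 8 = 4 months after the final one. Events in that overlap cannot have prevented re-infusion and count in both windows. The figures in Step 3 therefore describe the 75-day comparison only.

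**The case against.** The strongest reply is that the SAP never makes re-infusion depend on adverse events. The stated route to a second transplant is metabolic. The sentence in 3.7.8 concerns missing endpoint values, says only that some serious events may lead to withdrawal, and does not mention re-infusion. Several targeted events, such as oral ulcers or oedema, carry no stated consequence for it. This stands as a limit on size and scope: the bias belongs to particular event types, and neither its extent nor its direction can be read from the SAP. It does not restore the test, because withdrawal from study treatment is enough to remove a subject from the pairs.

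A second reply is that the SAP already reports initial-infusion incidence separately, lists premature terminations with reasons (3.4), gives the proportion re-infused (3.7.6.12), and calls its secondary analyses descriptive (3.7.2). This is largely right. However, none of it feeds the test or shows incidence by re-infusion status, and 3.8.2.1 still licenses a claim. For quality of life, 3.9.4.1.3 warns that causality cannot be inferred without a control group. The adverse-event comparison carries no such warning.

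Three stronger readings are tempting and not supported.
- A reader might infer that the trial understates first-infusion risk overall. The understatement is confined to the pairs.
- A reader might infer that the SAP will declare the later induction regimen worse. The rule claims a difference, without direction or attribution.
- A reader might infer that a random-intercept logistic model on all first and final infusions should replace the test. Fitted to trials of 48 subjects, its random-effect standard deviation fell to near zero in 34 to 61% of fits, with false claims of 6 to 9%. It also omits insulin independence and C-peptide, on which re-infusion does depend, and at 365 days it would count overlapping events twice.

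**Conclusion.** The point holds for event types that reduce the chance of re-infusion. For these, the 75-day McNemar test does not test equality of risk between the two infusions, and the SAP attaches a claim to it. The excess over the no-selection rate runs from one or two percentage points, when re-infusion falls from 0.60 to 0.45–0.48, to about 32 points uncorrected (36.9 − 4.4) when it falls to 0.15. All of this rests on an assumed 30% risk, equal at both infusions, and on assumed re-infusion probabilities. For rare events, or minor ones that do not alter re-infusion, the effect is negligible. At 365 days the same selection applies and the overlapping windows add a separate defect, so no error rate is put on that test. The primary endpoint is untouched. The change is worth making because it removes a potentially false safety claim at little cost.

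**What to change.** In 3.8.2.1:
- For each event type, show first-infusion incidence in all first-infusion recipients, split into re-infused and not re-infused, beside final-infusion incidence in the re-infused, with exact confidence intervals.
- Give the number not re-infused because of an adverse event.
- State that any paired result is conditional on having been re-infused.
- Delete the rule that claims a difference at p<0.05.

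In 3.8.2.2, delete the p<0.05 claim as well, and say that the windows after the first and final infusion overlap, so some events count in both.

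No replacement model need be mandated. The cost is SAP wording and a few table columns. The split uses adverse-event and infusion records the trial already holds, and the reasons for no further infusion can draw on the termination listing in 3.4. What is given up is a formal test that cannot bear the interpretation its context invites.
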